5.5 Circumstances That May Affect Study Product Delivery

If any of the following symptoms occur before or during SPI, they could indicate a serious clinical deterioration. If any of the following events/symptoms occurs, the procedure should be temporarily halted and the patient should be reevaluated for suitability to continue with the treatment under investigation:

1. Hypotensive episode defined as a sustained drop in blood pressure exceeding 20 mmHg not responsive to fluid administration
2. Hemodynamically significant arrhythmia requiring antiarrhythmic therapy
3. Two episodes of sustained ventricular tachycardia/ventricular fibrillation requiring cardioversion
4. Hemodynamically unstable
5. Fever (temperature increase to $\geq 100.4^{\circ}\text{F}$)
6. Cardiac perforation
7. Clinical signs and symptoms indicating a cerebrovascular accident

6.0 CLINICAL AND LABORATORY PROCEDURES

6.1 Schedule of Procedures (Table 3)

SENECA Study Procedure	BSL	D0 (SPI)	D1	Wk1 (+/-3 days)	M1 (+/-7 days)	M6 (+/-30 days)	M12 (+/-30 days)	M24 (+/-30 days) Call ₇
Informed Consent	X							
Complete Medical History	X							
Physical Exam	X	X	X	X	X	X	X	
Vital Signs	X	X ₁	X	X	X	X	X	
Adverse Events	X	X	X	X	X	X	X	
Con Medications	X	X	X	X	X	X	X	
NYHA	X				X	X	X	
MLHFQ	X					X	X	
12-lead ECG	X	X ₂	X ₂	X		X	X	
Stress Echo	O							
2D Echoes		X ₂						
Telemetry		X ₃						
Labs and Biomarkers (PB)₄	X	X	X	X	X	X	X	
Cardiac MRI	X					X	X	
ICD Interrogation₅	X	X				X	X	
6 Minute Walk	X					X	X	
Randomization	X							
Catheterization / NOGA		X						
Temp. Log			X ₆					

Telephone Interview								X
---------------------	--	--	--	--	--	--	--	---

O= indicates optional test; dependent upon available imaging in the patient chart to assess CAD.

Baseline testing, randomization, and SPI will take place within 45 days of ICF.

1. Subjects will have assessments of vitals (BP, temperature, pulse rate) pre- and post-procedure.
2. ECGs will be performed within 6 hours following the catheterization procedure and again before discharge; a 2-D echocardiogram will be performed post SPI (within 6 hours).
3. Subjects will be monitored on simple telemetry up to 24 hours post-procedure or until discharge, whichever is sooner.
4. See section 6.3 for specific tests done at each time point.
5. ICD interrogation (if applicable) done before and after every MRI as part of MRI protocol as well as before the SPI procedure.
6. Temperature log 2x/day x 7 days.
7. 24-Month contact is a telephone visit only.

6.2 Baseline Testing

See Table 3 above for the procedures and assessments to be performed during this phase of the study. All baseline tests, procedures, and randomization, will occur within 45 days of signing informed consent form (ICF). No baseline testing will take place until the subject is fully informed of the research and signs the ICF unless the evaluations were being performed as part of routine medical care. After the subject has consented to the study, the subject will have a series of assessments to establish eligibility to receive study product. Randomization will take place after subject eligibility has been determined.

Subjects will undergo the following tests and procedures during the baseline testing period:

1. Comprehensive medical and surgical history, including smoking history and notation of the cumulative dose of anthracycline, time from anthracycline exposure to development of HF, and the time from diagnosis of HF to study enrollment
2. Concomitant medication and adverse event assessment
3. Physical examination including systems review
4. Vital signs (blood pressure [BP], temperature, heart rate, respiratory rate)
5. Height and weight
6. NYHA class assessment (Appendix B)
7. Questionnaire: Minnesota Living with Heart Failure Questionnaire (MLHFQ) (Section 6.6.2)
8. cMRI (Section 6.6.3, MRI Core Lab Manual of Operations)
9. ICD interrogation (if applicable). Reports will be generated for the interrogations conducted before the MRIs at baseline and at the 6 month and 12 month visits. Local electrophysiology personnel will review the device report for the presence of reportable clinical events. Copies of the reports should remain on site as source documentation (de-identified copies may be requested by the Sponsor for endpoint adjudication).
10. A 6-minute walk test (6MWT) (Section 6.6.1, Protocol Manual of Operations)
11. 12-lead ECG
12. Laboratory evaluations (Section 6.3) including pregnancy test on women of childbearing potential only
13. For participants with no recent (within past 5 years) available imaging to assess CAD, and for which an updated test is not otherwise authorized under a patient's insurance under standard of care, a stress echo will be obtained as part of the baseline testing and paid for by the study, to be reviewed for eligibility. This test should only be done, if recent imaging is not otherwise available or obtainable.

6.3 Schedule of Laboratory Examinations (Table 4)

Table 4. Laboratory Testing	BSL	Day 0 (SPI)	Day 1 ₁₁	Wk 1	M 1	M 6	M 12
CMP/Chemistry Tests ₁	X	X	X	X	X	X	X
CBC with Differential ₂	X	X ₆	X	X	X	X	X
Panel of reactive antibodies (PRA)	X				X	X	X
Liver Function Tests ₃	X					X	X
Pregnancy (childbearing women)	X	X ₄				X	X
NT-proBNP ₅	X					X	X
Troponin I or T	X	X ₆	X	X			
HbA1c	X					X	X
PT, INR, PTT ₇	X	X ₁₂					
Infectious Disease Tests ₈	X						
Peripheral Blood Collection (Biorepository) ₉		X ₁₀	X	X	X	X	

1. Complete Metabolic Panel/Chemistry Tests - sodium, potassium, chloride, bicarbonate (CO₂), glucose, blood urea nitrogen (BUN), creatinine, and eGFR
2. Complete Blood Count with Differential - CBC: WBC, RBC, hemoglobin, hematocrit, MCV, and platelets; Diff: neutrophils, lymphocytes, monocytes, eosinophils, and basophils
3. Liver Function Tests - albumin, alkaline phosphatase, alanine transaminase (ALT), aspartate transaminase (AST), total bilirubin, direct bilirubin, and total protein
4. Will be completed within 36 hours prior to injection
5. NT-proBNP required; send to outside lab if applicable.
6. Will be performed once in the morning and once 8 (+/- 2) hours post cardiac catheterization/NOGA
7. Later time points if indicated
8. Infectious Disease Tests – HBc, HBsAg, HBV, HCV, HIV-1 groups M&O RNA, and Anti-HIV
9. With appropriate consent, twenty (20) mL of peripheral blood will also be collected and transported to the CCTRN biorepository for scientific study (See Section 6.7 Collection of Biospecimens)
10. Collected prior to sedation for the SPI procedure
11. Day 1 labs will be collected 24 hours post-procedure or immediately prior to discharge, whichever is sooner
12. For subjects receiving systemic anticoagulation therapy, an INR measurement will be performed on the morning of the planned procedure; must be <1.6 to proceed with SPI

6.4 Day of Study Production Injection (SPI) – Day 0

For subjects receiving systemic anticoagulation therapy, an INR measurement will be performed on the morning of the planned procedure. Research teams should follow institutional and interventionalist standard of practice for managing anticoagulation before the SPI procedure. The following guideline could also be used. *Anticoagulation management guideline*: Stop warfarin 4 days prior to the date of planned SPI. Careful consideration for bridging anticoagulation should be given to assess risk of occurrence of thrombotic events for subjects off anticoagulation.¹¹² Perform INR measurement on morning of planned procedure. **Require an INR of < 1.6 for these subjects to proceed with SPI.** For subjects on Factor Xa inhibitors, stop 2 days prior to planned SPI procedure.

1. Incremental medical history
2. Physical exam including vitals (BP, temperature, pulse rate) and weight
3. Laboratory examinations (see section 6.3)
4. ICD interrogation prior to SPI
5. Cardiac catheterization and injection of study product (see section 5.4) including vitals (BP, temperature, pulse rate) immediately pre- and post

6. 12-lead ECG will be performed within 6 hours following the catheterization procedure and again before discharge
7. A 2-D echocardiogram will be performed post SPI (within 6 hours). Additional echocardiographic assessments for pericardial effusion will be done only as clinically indicated.

6.5 Follow-up Tests Performed After SPI

Randomized subjects will be followed up at 1 week and 1, 6, and 12 months after study product injection for regular history and clinical examination. The MLHFQ will be repeated at 6 and 12 months after SPI. To further evaluate their functional capacity, subjects will also undergo a 6MWT at 6 and 12 months after SPI. Subjects will be assigned a functional class during the month 1, 6, and 12-month follow-up visits based on the standard NYHA classification. Patients treated with allo-MSCs or placebo will undergo the following tests at various time points after the procedure (Table 3):

6.5.1 Day 1 (within the first 24 hours after SPI)

1. Subjects will be monitored on simple telemetry up to 24 hours post-procedure or until discharge, whichever is sooner.
2. Incremental medical history
3. Physical exam including vitals (BP, temperature, pulse rate)
4. Laboratory examinations (Section 6.3)
5. 12-lead ECG will be performed within 6 hours following the catheterization procedure and again before discharge
6. The subject will keep a daily temperature log for seven days following the catheterization procedure to help assess the early development of an infection.

6.5.2 Week 1 (\pm 3 days after SPI)

1. Incremental medical history
2. Physical exam including vitals (BP, temperature, pulse rate) and weight
3. Laboratory examinations (Section 6.3)
4. 12-lead ECG
5. Collect temperature log from subject

6.5.3 Month 1 (\pm 7 days after SPI)

1. Incremental medical history
2. Physical exam including vitals (BP, temperature, pulse rate) and weight
3. Laboratory examinations (section 6.3)
4. NYHA classification (Appendix B)

6.5.4 Month 6 (\pm 30 days after SPI)

1. Incremental medical history
2. Physical exam including vitals (BP, temperature, pulse rate) and weight
3. Laboratory examinations (see section 6.3)
4. NYHA classification (Appendix B)
5. cMRI (Section 6.6.3, MRI Core Lab Manual of Operations)
6. Questionnaire: MLHFQ (Section 6.6.2)
7. 12-lead ECG
8. 6MWT (Section 6.6.1, Protocol Manual of Operations)

6.5.5 Month 12 (± 30 days after SPI)

1. Incremental medical history

CONFIDENTIAL AND PROPRIETARY

2. Physical exam including vitals (BP, temperature, pulse rate) and weight
3. Laboratory examinations (Section 6.3)
4. NYHA classification (Appendix B)
5. cMRI (Section 6.6.3, MRI Core Lab Manual of Operations)
6. Questionnaire: MLHFQ (Section 6.6.2)
7. 12-lead ECG
8. 6MWT (Section 6.6.1, Protocol Manual of Operations)
9. A standard of care visit with subject oncologist (or post-cancer follow-up care provider) within 3 months after study completion (to assess cancer recurrence during the study period).

6.5.5.1 Transplants, CRT, or LVADs before Months 6 or 12

If subjects are transplanted, receive CRT, or receive an LVAD prior to the month 6 or 12 visits, every attempt should be made to collect the endpoint measures (see Section 3.6.2) before transplant, CRT, or LVAD procedure. Labs and pathology (explanted heart) will be collected from those providing appropriate consent (see Section 6.7.3).

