3.2 Study Design

This study will evaluate approximately thirty-six subjects. The first six subjects will receive allo-MSC therapy (open label) and will be assessed for safety and feasibility of the study procedures. Following 1 month data review of each of the six subjects by the NHLBI Gene and Cell Therapy Data and Safety Monitoring Board; this will be followed by a randomized, double-blind clinical trial enrolling approximately thirty subjects (see Section 7.7). These subjects will be randomized 1:1 to receive allo-MSCs or placebo. All subjects will undergo cardiac catheterization and study product administration using the NOGA Myostar catheter injection system. Subjects will be followed at 1 day, 1 week, 1 month, 6 months, and 12 months post study product injection. All endpoints will be assessed at the 6 and 12 month visits which will occur 180 ± 30 days and 365 ± 30 days, respectively, after the day of study product injection (Day 0).

For the purpose of the safety evaluations and endpoint analysis, we will utilize an “intention-to-treat” study population. In addition, because this phase I study is the first cell therapy study in this population, at 12 months all available standard-of-care medical records for cancer surveillance will be reviewed for cancer recurrence. Approximately thirty-six subjects will be enrolled over a 12-18 month accrual period.

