3.4 Study Endpoints

3.4.1 Safety Assessment

To demonstrate the relative safety of allo-MSCs when compared with placebo, the following safety data will be collected and analyzed by therapy group between baseline and a) 6 months and b) 12 months:

1. Major adverse cardiac events (MACE) including death, hospitalization for worsening heart failure (HF), and/or exacerbation of HF (non-hospitalization)
2. Other significant clinical events including non-fatal stroke, non-fatal myocardial infarction, coronary artery revascularization, ventricular tachycardia/fibrillation, pericardial tamponade, infectious myocarditis, hypersensitivity reaction, neoplasm, or any other potential deleterious late effects detected and corroborated by clinical presentation, laboratory investigations, image analysis, and when necessary with biopsy from suspected target sites in the body
3. All adverse events (AEs) at least grade 2 in severity (see section 7.3.1)

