6.5.6 Month 24 Telephone Contact

A Month 24 telephone contact will be made to assess current medications, as well as morbidity and mortality in study subjects.

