6.5.8 Lost to Follow-up

Randomized subjects will be followed for up to two years. Subjects will be considered lost to follow-up after 3 consecutive failed telephone contacts AND one certified letter returned to the site. Contact attempts will be documented in the subject's study chart.

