7.3 Reporting Responsibilities of the Investigator

For all events (AE/SAR and SAE/SSAR), monitoring and reporting to the DCC begins at the time that the subject provides informed consent, which is obtained prior to the subject's participation in the study, i.e., prior to undergoing any study related procedure and/or receiving investigational product, through and including 30 calendar days after the subject completes the 12-month clinic visit. Events should be recorded on the Adverse Event electronic case report form (eCRF). Do not delay the initial reporting of an event in order to obtain resolution or follow up information.

For all events, the Investigator must pursue and obtain adequate information both to determine the severity and causality of the event. For events with a causal relationship to the investigational product, follow-up by the Investigator is required until the event or its sequelae resolve or stabilize at a level acceptable to the Investigator, and the DCC concurs with that assessment.

In the event that the Investigator does not become aware of the occurrence of a SAE/SSAR immediately (i.e., if an outpatient study subject initially seeks treatment elsewhere), the Investigator is to report the event within 24 hours after learning of it and document the time of his/her first awareness of the event.

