8.3.2.1 Safety Evaluations

To demonstrate the relative safety of allo-MSCs when compared with placebo, the following analyses will be carried out, and the data tabulated and analyzed by therapy group (Fisher's Exact Test) between baseline and a) 6 months and b) 12 months:

1. Major adverse cardiac events (MACE) including death, hospitalization for worsening heart failure (HF), and/or exacerbation of HF (non-hospitalization)
2. Other significant clinical events including non-fatal stroke, non-fatal myocardial infarction, coronary artery revascularization, ventricular tachycardia/fibrillation, pericardial tamponade, infectious myocarditis, hypersensitivity reaction, neoplasm, or any other potential deleterious late effects detected and corroborated by clinical presentation, laboratory investigations, image analysis, and when necessary with biopsy from suspected target sites in the body
3. All adverse events (AEs) at least grade 2 in severity (see section 7.3.1)

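### Event reporting closes 30 days after the 12-month visit, but the oncologist visit meant to find recurrence may come up to 3 months after study completion, so a recurrence learned of there could be left out of the safety tables

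*Combined protocol and SAP*

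**What the plan says.** Section 3.4.1 lists neoplasm in the second of its three safety items, within the run "hypersensitivity reaction, neoplasm, or any other potential deleterious late effects". Section 8.3.2.1 has these items "analyzed by therapy group (Fisher's Exact Test) between baseline and a) 6 months and b) 12 months".

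Three provisions bear on how a recurrence reaches those tables.

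- Section 6.5.5, item 9, schedules "A standard of care visit with subject oncologist (or post-cancer follow-up care provider) within 3 months after study completion". Its stated purpose is to assess recurrence during the study period. Study completion is not defined.
- Section 7.3 has all events monitored and reported to the coordinating center from consent "through and including 30 calendar days after the subject completes the 12-month clinic visit". For a serious event that the investigator did not hear of at once, it adds that "the Investigator is to report the event within 24 hours after learning of it".
- Section 3.2 says that "at 12 months all available standard-of-care medical records for cancer surveillance will be reviewed for cancer recurrence". This review is not repeated in section 6.5.5 or in Table 3.

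There is also a later call (section 6.5.6): "A Month 24 telephone contact will be made to assess current medications, as well as morbidity and mortality in study subjects". Table 3 marks no adverse event collection at that contact.

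**The concern.** Section 2.3 treats tumor recurrence as a major worry for cell therapy after cancer. Item 9 is the only visit in section 6.5 devoted to recurrence. It is a standard-of-care visit with the subject's own oncologist, so what it finds has to be passed to the study site and then entered as study data.

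The two timing rules do not fit together. A visit whose purpose is to find recurrence from the study period may take place after the site's stated duty to report events has ended. A site that follows section 7.3 to the letter need not report a non-serious recurrence it learns of there. No section says how the visit's result is recorded, which date it takes, or how it enters the neoplasm count. With about 15 subjects per arm, a single case decides whether that row reads none or one.

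**Working it through.** The plan gives no figure of its own on this point, so the check is day arithmetic on its windows.

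**Inputs.** The 12-month visit V is at day 365 ± 30, so day 335 to 395 (section 6.5.7). Reporting closes at V + 30 (section 7.3). The oncologist visit may fall up to 3 months after study completion (section 6.5.5). I take 3 months as 91 days and completion as the 12-month visit. The arms have 15 subjects each (Executive Summary), with 6 cell-treated lead-in subjects added in the total cohort (section 8.3.2).

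**Step 1: the gap.**

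| 12-month visit | Reporting closes (V + 30) | Oncologist window ends (V + 91) | Days after closure |
|---|---|---|---|
| Day 335 | Day 365 | Day 426 | 61 |
| Day 365 | Day 395 | Day 456 | 61 |
| Day 395 | Day 425 | Day 486 | 61 |

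The share of the window after closure is (91 − 30)/91 = 61/91 = 67%. With 3 months as 90 or 92 days it is 60/90 = 66.7% or 62/92 = 67.4%. These are shares of permitted days, not of visits or recurrences.

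**Step 2: which recurrences are affected.** The earliest closure is 335 + 30 = day 365. So for a visit held within its window, a recurrence diagnosed by day 365 always occurs inside the reporting window. It can be lost only if the site learns of it after closure. A recurrence first diagnosed at a late oncologist visit falls after month 12 and does not belong in the 12-month table. It belongs in the safety report, where the plan has no place for it.

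**Step 3: what one lost in-window case does.** Exact (Clopper-Pearson) 95% intervals:

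| Group | Case recorded | Case not recorded |
|---|---|---|
| One arm | 1/15 = 6.7% (0.2 to 31.9%) | 0/15 (0 to 21.8%) |
| Cell-treated, total cohort (15 + 6 = 21) | 1/21 = 4.8% (0.1 to 23.8%) | 0/21 (0 to 16.1%) |

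Fisher's exact p for 1/15 against 0/15 is 1.0, so this one case does not move the test. The loss is in the description of safety.

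**Step 4: scale, as context only.** Section 4.3 admits subjects with a five-year recurrence risk p of up to 30%. Assume a constant hazard, so that S(d) = (1 − p)^(d/1826.25), and that all 36 subjects share the same p; 10% is an assumed lower value.

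- Expected by month 12, 36 × [1 − S(365)]: 2.48 at p = 0.30 and 0.75 at p = 0.10.
- Expected first diagnoses in days 31 to 91 after a day-365 visit, 36 × [S(395) − S(456)]: 0.39 and 0.12.

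Neither line estimates missed cases. They show only that few recurrences are expected.

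**The case against.** The strongest reply is that two data streams are being merged. Section 7.3 governs adverse event reporting, whereas neoplasm sits in a safety item listed apart from adverse events of grade 2 or more, and no section says that item's data close on day 30. Naming the oncologist visit as a month 12 procedure with a stated purpose suggests that its result is meant to be used. The case report forms are not in the documents, so the lack of a form cannot be inferred. This stands as far as it goes: one can say that a case could be left out, not that it will be. But section 7.3 covers all events, and no other route for the visit's result is described.

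Partial routes also exist. History, examination and adverse event collection run through month 12. The section 3.2 records review looks back and should recover most charted cases. Section 7.1.3 lets the investigator or the coordinating center class an important medical event as serious, and a recurrence could often qualify. The rule for late-learned events may then apply, although it covers serious events only and does not say whether it holds after day 30. The order of the records review and the oncologist visit is not fixed. They can be read as one month 12 assessment, but nothing requires the review to wait for the visit.

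A reader might infer from section 6.5.8 ("Randomized subjects will be followed for up to two years") that completion means the 24-month call, which would put the whole oncologist window after closure. The placing of the visit under month 12 makes that the less natural reading, and the point does not need it. A reader might also infer that a chart review is needed at month 6 or at early exit. That is a separate preference and does not follow from this gap.

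**Conclusion.** The conflict is between two stated rules, and it holds. Taking completion as the 12-month visit, about two thirds of the permitted oncologist-visit days lie after event reporting has closed. A recurrence learned of in that stretch, above all one not classed as serious, is outside the stated reporting window and could be missing from the safety tables.

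The stronger claim, that such a recurrence has no route into the data, is not supported: the routes are partial, not absent. Nor do the documents allow an estimate of how many cases would be lost. The interval changes in Step 3 apply only to a case diagnosed by month 12 and learned of after closure.

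The point is minor to moderate. It concerns the completeness and dating of a primary safety component and has no bearing on the design, the sample size or power.

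**What to change.** 1. In section 7.3, extend reporting of neoplasm and recurrence, serious or not, through the section 6.5.5 oncologist visit.
2. Date each case by its diagnosis. Count those diagnosed by month 12 in the 6- or 12-month table according to that date, and list later ones on a separate line by arm.
3. In section 6.5.5, define study completion as the 12-month visit.
4. Complete the section 3.2 records review after the oncologist visit, so that the review includes that visit's record.

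The cost is wording, plus one event form kept open about two months (61 days) longer per subject. The latest window end, day 486, still comes well before the 24-month call at day 700 to 760, so follow-up is not lengthened. No new test or visit is needed.
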